Entry Criteria	X		Х									
Medical History	Х							Х	Х	Х	Х	
Physical Exam	Х											
Body Weight	Х		Х					Х	Х	Х	Х	
ECĞ	Х											
Hematology and chemistry	Х										Х	
Lipids	Х										Х	Х
HbA1c	X							Х	Х	Х	X	X
Fasting plasma glucose	Х							Х	Х	Х	Х	Х
Postural Blood Pressure								X	X	X	X*	
Aortic compliance testing		Х										X*
DXA for body composition measurements				X							Х	
Assessment of endothelial function using Endo-PAT			X ¹								X ¹	
Blood sample for measurement of inflammatory biomarkers and isolation of WBCs				Х								Х
Mixed Meal Tolerance test			Х								Х	
Ambulatory BP monitoring device set up			X	Return ABPM device							X	Return ABPM device
24-hour urine collection instruction			Х	Return 24 hour urine							Х	Return 24 hour urine
Cycloset Titration				X (first dose same day as visit 3)	х	х	х					Discontinue Cycloset
Concomitant meds	To be assessed throughout the study											
Adverse Events	To be assessed throughout the study											
Hypoglycemia	To be assessed throughout the study											
Serious Adverse Events	To be assessed throughout the study Report serious adverse events to sponsor within 24 hours											
Mandatory Contact	Weekly titration phone contacts as described in the protocol											

Endo-PAT conducted upon arrival to study site and at 90 minutes into the Mixed Meal Tolerance test

* These tests (DXA and Aortic compliance testing) may be done on either Visit 7 or Visit 8

Mixed MEAL TOLERANCE TEST

		3-3H-Glu/					
Time	Glucose		C-pep/Ins	Glucagon	FFA	GLP-	1/GIP
(minutes)	(0.5 ml)	(6 ml)	(3 ml)	(2 ml)	(2 ml)	(3 ml) (2 ml)
-180	X	X	X	X	X	X	
-180	start 3-3H-glud	ose					
-30	Χ	X*					
-20	Χ	X*	Χ	X	Χ		Χ
-10	X	X*	Χ	X	Χ		Χ
-5		X*					
0	X	X*	Χ	X	Χ		ХХ
0	Mixed meal with 1-1-glucose	4C-					
15	X	X	Χ				
30	X	X	Χ	X	Χ		
45	X	X	Χ				
60	X	X	Χ	X	Χ		Χ
75	X	X	Χ				
90	X	X	Χ	X	Χ		
105	X	X	Χ				
120	X	X	Χ	X	Χ		Χ
135	X	X					
150	X	X	Χ	X	Χ		
165	X	X					
180	X	X	Χ	X	Χ		
195	X	X					
210	X	X	Χ	X	Χ		
225	X	X					
240	X	X	Χ	X	Χ		Χ
255	X	X	Χ	X	Χ		
270	Χ	X	X	X	Χ		
285	X	X	X	Χ	X		
300	Χ	X	X	X	Χ		
Number	26	26	21	16	16	3	5
Blood volume (ml)	13	156	63	32	32	9	10

Total blood loss (ml) = 315 ml

^{* 3-3}H-glucose only

ABBREVIATIONS AND DEFINITIONS

ABPM Ambulatory Blood Pressure Monitoring

AE Adverse Event

BG Blood Glucose

BMI Body Mass Index

CRC Clinical Research Center

CRF Case Report Form

DM Diabetes Mellitus

FPG Fasting Plasma Glucose

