2 STUDY OBJECTIVES

2.1 PRIMARY OBJECTIVE

The objective of this study is to examine the effect of the addition of Cycloset on glycemic control in inadequately controlled (HbA1c 7.5-10.0) T2DM patients who are already on Bydureon (exenatide once weekly) or Victoza (liraglutide) as part of their standard care.

An additional co-primary objective of the study is to examine the effect of Cycloset on postprandial glucose metabolism.

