Subjects will be rested in the supine position for 15 minutes. Measurements for the assessment of aortic pulse wave velocity (PWV) will then be taken immediately after measurement of brachial blood pressure. PWV is determined by simultaneous measurement of arterial pressure waves at the carotid and femoral arteries with sensitive pressure transducers place on the skin overlying the carotid and femoral arteries. This is a completely noninvasive procedure using previously described and published techniques (Circulation 2006; 113: 1213-1225). The surface distance from suprasternal notch to the distal (femoral) recording site is measured, and the pressure wave transit time is calculated using a foot-of-the-wave to foot- of-the-wave method. PWV is calculated by dividing the distance to the distal site by the pressure wave transit time. Data are collected by a single trained observer, and the mean of at least 2 PWV measurements is taken for each subject.

Meal Tolerance Test (MMT)

Following a 10-12 hour overnight fast, catheters will be placed in the antecubital vein or hand vein, one for infusion of tritiated glucose and one for blood withdrawal. At -180 minutes baseline blood samples (see attached flow sheet) will be obtained and a prime (40 uCi x FPG/100) – continuous (0.40 uCi/min) will be started. Blood samples for determination of plasma, glucose, insulin, C-peptide, glucagon, FFA, glucagon-like peptide-1, and glucose-dependent insulinotropic polypeptide and tritiated glucose and 14C-glucose radioactivity will be obtained at -180, -30, -20, -10, and 0 minutes. At time zero subjects will ingest a mixed meal (75 grams of glucose, 25 grams of fat, 20 grams of protein, 600 kcal) over 15-20 minutes. The glucose will be labeled with

100 uCi of 1-14C-glucose. Plasma samples for substrates, hormones, and radioactivity will be obtained every 15 minutes for 5 hours. Plasma samples for catecholamines (CA) will be collected at -10, 0, 60, 120, and 240 minutes.

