Meal tolerance will be determined by calculating the glucose AUC (trapezoidal rule) during the MTT. Insulin secretion will be calculated as I0-300/G0-300, CP0-300/G0-300, and ISR0-300/G0-300, where ISR = insulin secretary rate (deconvolution of the plasma C-peptide curve). Beta cell function (11) will be calculated as the insulin secretion/insulin resistance (disposition) index: ISR0-300/G0-300 x Matsuda Index of insulin sensitivity (12). The same measures will be examined for the following time intervals: -10, 0, 0-60, 0-120, 0-180, and 0-240.

During the fasting postabsorptive state, the rate of HGP equals the rate of glucose uptake by all tissues in the body and is calculated as the tritiated glucose infusion rate (DPM/min) divided by the plasma tritiated glucose specific activity (DPM/mg). Following meal ingestion, non-steady state conditions prevail and the rates of total (RaT) and oral (RaO) glucose appearance in the systemic circulation are calculated using Steele's equation from the 14C-glucose and 3H-glucose specific activities, respectively, as previously described (13). The difference between RaT and RaO yields the rate of endogenous HGP. Subtraction of RaO from 75 grams (ingested glucose load) gives the splanchnic (primarily reflects) glucose uptake.

Dual-Energy X-ray Absorptiometry (DXA)

After an overnight fast, a DXA scan for body composition scan will be performed using a Hologic DXA scanner. Subjects will be resting comfortably in supine position in a quiet room and the entire body will be scanned. The acquired images will be integrated and analyzed by a software IBM computer program and total amount of fat and fat-free mass and total body water will be estimated. Total and regional fat and fat-free mass will be measured by a licensed radiology technician using a Discovery 010-1596 instrument from Hologic that is housed on the CRC at the Texas Diabetes Institute.

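### The post-meal tracer sentence assigns the two isotopes the wrong way round, so post-meal hepatic glucose production and splanchnic uptake would be invalid if it were followed

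*Combined protocol and SAP*

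**What the plan says.** The Meal Tolerance Test part of section 3.1 places two catheters, "one for infusion of tritiated glucose and one for blood withdrawal". Tritiated (3H) glucose is given as a prime, then at 0.40 uCi/min from -180 minutes. At time zero the subject eats a meal with 75 g of glucose, labelled with "100 uCi of 1-14C-glucose". The meal-test table in the Study Schedule agrees: 3H starts at -180 minutes, 14C comes with the meal, and a footnote restricts the starred samples from -30 to 0 minutes to the infused label ("H-glucose only").

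Fasting hepatic glucose production (HGP) is the 3H infusion rate divided by the plasma 3H specific activity. For the period after the meal, section 3.1 then states that "total (RaT) and oral (RaO) glucose appearance in the systemic circulation are calculated using Steele's equation from the 14C-glucose and 3H-glucose specific activities, respectively", and cites an earlier paper for the method. Two quantities follow from these rates. The first is HGP: "The difference between RaT and RaO yields the rate of endogenous HGP". The second is splanchnic glucose uptake, obtained by subtracting RaO from the 75 g load.

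Section 2.1 gives the outcome its standing: "An additional co-primary objective of the study is to examine the effect of Cycloset on postprandial glucose metabolism". Section 7.3.1 lists change in postprandial glucose metabolism as primary efficacy data. Section 10.1 leaves the details of analysis to a SAP that will be finalized before database lock.

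**The concern.** A label that enters the body only with the meal can trace only meal glucose. A label infused into a vein is diluted by all glucose entering the circulation, so it traces total appearance. The sentence pairs them the other way, and the word 'respectively' allows no other reading. It also conflicts with the fasting rule just before it, which uses 3H correctly.

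No other place in the documents corrects the pairing, and it is the only assignment of isotopes to post-meal rates that they contain. Post-meal HGP and splanchnic uptake both depend on it. They are two of several unranked measures under the co-primary postprandial objective, and section 1 gives inhibition of post-meal HGP as part of the rationale for the combination.

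Two smaller gaps sit beside it. The 14C specific activity of the meal glucose, needed to turn plasma 14C into a rate of oral appearance, is not mentioned. And RaO, defined as a rate, is subtracted from an amount in grams without a statement that it is integrated over time.

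**Working it through.** The documents give no numerical RaT, RaO, HGP or uptake, so there is no figure to reproduce. The check is algebra, with illustrations on assumed physiology.

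**Inputs from section 3.1** (1 uCi = 2.22 × 10^6 DPM)
- 3H infusion: 0.40 × 2.22 × 10^6 = 888,000 DPM/min.
- Meal 14C specific activity, nominal: 100 × 2.22 × 10^6 / 75,000 mg = 2,960 DPM/mg.
- 14C infusion: none.

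**Reading (a): correct rates, labels exchanged.** Here the written RaT is the true RaO, and the reverse.
- HGP as written = RaO − RaT = −HGP.
- Uptake as written = 75 − RaT = (75 − RaO) − HGP = true uptake − HGP.

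This needs no physiological assumption. For a sense of size, assume 0–300 min RaO of 50, 60 or 65 g and HGP of 20, 30 or 40 g:

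| RaO (g) | True uptake (g) | As written, HGP 20 g | As written, HGP 30 g | As written, HGP 40 g |
|---|---|---|---|---|
| 50 | 25 | +5 | −5 | −15 |
| 60 | 15 | −5 | −15 | −25 |
| 65 | 10 | −10 | −20 | −30 |

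Uptake is negative in 8 of the 9 cells, and signed HGP is −20 to −40 g. A simulation on other assumptions (weight 80–110 kg, fasting glucose 170 mg/dL, fasting HGP 2.2 mg/kg/min, 67–82% of the meal glucose reaching the circulation by 300 min) agrees. Over four scenarios, HGP is −25.9 to −38.0 g instead of +25.9 to +38.0 g, and uptake is −9.9 to −20.6 g instead of 13.8 to 24.6 g.

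**Reading (b): Steele's equation applied literally to 14C.** With infusion rate F, pool volume pV, plasma glucose C and specific activity SA, Steele gives Ra = [F − pV × C × dSA/dt] / SA. For 14C, F = 0, so RaT as written = −pV × C × (dSA14/dt) / SA14. This is negative while 14C specific activity rises and positive once it falls. RaO as written is Steele on 3H, which is the true RaT.

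One-pool simulation, all inputs assumed: RaO 60 g, HGP 30 g over 300 min (basal 160 mg/min falling to 93), fasting glucose 160 mg/dL, pV 14.6 L, absorption peak 60 min. Values in mg/min:

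| Minute | True RaT | RaT as written | True HGP | HGP as written |
|---|---|---|---|---|
| 30 | 434 | −1237 | 118 | −1670 |
| 60 | 486 | −461 | 102 | −947 |
| 120 | 377 | −97 | 95 | −474 |
| 240 | 170 | +43 | 93 | −127 |

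Over pV 10–20 L and absorption peak 40–80 min, the 30-minute RaT as written runs from −746 to −1802 and the 240-minute value from +3 to +75.

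**Deriving the correct pairing.** Let SA3 and SA14 be the plasma specific activities and Rd the rate of disappearance.
- Steele on the infused label: RaT = [888,000 − pV × C × dSA3/dt] / SA3.
- 14C balance: d(pV × C × SA14)/dt = RaO × SAmeal − Rd × SA14.
- Glucose balance: pV × dC/dt = RaT − Rd.
- Eliminating Rd: RaO = [RaT × SA14 + pV × C × dSA14/dt] / SAmeal.

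On the simulated data these return RaT 90.0 g, RaO 60.0 g and HGP 30.0 g in all nine combinations of pV (10, 14.6, 20 L) and peak (40, 60, 80 min). Because the same one-pool model generated the data, this confirms the algebra and says nothing about how well a one-pool model fits patients.

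**The case against.** The strongest reply is that this is a slip of wording. Section 3.1 fixes what each tracer does, staff who run dual-tracer studies would compute the rates correctly, and the method is deferred to a cited paper and a later SAP. That is probably so, but the cited paper cannot be checked here, and a citation does not cure an explicit pairing that contradicts the tracers this protocol gives.

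Several narrower points stand.
- If labels are exchanged and the difference is taken without its sign, HGP is correct and only uptake is wrong.
- Errors would be easy to detect by comparing rates: with exchanged labels and positive HGP, cumulative oral appearance always exceeds total. Even the +5 g case, plausible as an uptake on its own, has 70 g oral against 50 g total.
- Reading (b) is one that few analysts would adopt, and its figures rest on assumed inputs.
- The documents do not name HGP or splanchnic uptake as the co-primary variable. Glucose AUC, the stated measure of meal tolerance, is unaffected.
- The counts for both isotopes are kept, so the rates can be recalculated.
- The cited method may cover the meal specific activity, the pool term and integration, and subtracting from 75 g already implies an amount.

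These points bear on weight. None makes the sentence correct.

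**Conclusion.** The concern holds. As written, the sentence contradicts the protocol's own tracer design, and neither reading gives valid values for both post-meal HGP and splanchnic uptake. Under exchanged labels the error is exact and free of assumptions: signed HGP changes sign, and uptake is too low by the cumulative HGP. The error in uptake of 20 to 40 g rests on the assumed HGP range, as do the other gram figures on their inputs.

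The scope is limited to post-meal RaT, RaO, HGP and splanchnic uptake. HbA1c, glucose AUC, the insulin-secretion indices, fasting HGP and the sample size are not touched. It should be fixed because it is a stated calculation rule for part of a co-primary outcome. It is not a threat to the data collected.

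**What to change.** Correct the sentence in section 3.1 and put the same formulas in the SAP before database lock:
- RaT from Steele's non-steady-state equation, using the 3H infusion rate and plasma 3H specific activity.
- RaO = [RaT × SA14 + pV × C × dSA14/dt] / SAmeal, with the same pool term as for RaT and its value stated. SAmeal is nominally 2,960 DPM/mg (100 uCi / 75 g = 1.33 uCi/g), and is better measured.
- HGP = RaT − RaO, as a signed difference.
- Splanchnic uptake = 75 g minus RaO integrated over 0–300 minutes.

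Exchanging the two isotope names alone is not enough, because RaO also needs the meal specific activity and the 3H-derived RaT. A routine check that cumulative RaO does not exceed cumulative RaT would catch any remaining exchange.

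The cost is one corrected sentence and the matching SAP text. Both isotopes are already in the sampling schedule, so no visits or subjects are added. Measuring SAmeal would take one meal aliquot per test.

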3.2 STUDY DURATION AND DATES

The duration of this study is expected to be 18 months, with subject recruitment proposed to start in May 2014 and end in October 2015. The actual overall study duration or subject recruitment period may vary.

4 SELECTION OF SUBJECTS

4.1 NUMBER OF SUBJECTS

15 subjects

4.2 INCLUSION CRITERIA

- 1. Type 2 diabetes male or female subjects between the ages of 30 and 70 years of age, inclusive, at Screening
- 2. BMI = 24-40 kg/m2
- 3. HbA1c = 7.5-10.0%
- 4. Stable body weight (±3-4lbs) over the preceding 3 months
- Subjects currently receiving a stable dose of exenatide (2mg/week) or liraglutide (1.2-1.8 mg/day) for at least 90 days prior to determination of baseline A1C and eligibility for enrollment in the study protocol.
- 6. Subjects with a daytime feeding/night time sleeping schedule
- 7. Subjects with no evidence of major organ system disease as determined by physical exam, history, and screening laboratory data
- 8. Women must be of non-childbearing potential as defined by one of the following:
 - a. Women >45 and < 60 years of age at Screening, who have been amenorrheic for at least 2 years
 - b. Women who have had a documented hysterectomy and/or bilateral oophorectomy
 - c. Women > 60 years of age
- 9. Females of childbearing potential with a negative pregnancy test at Screening and using one of the following forms of contraception for the duration of participation in the study (i.e., until Follow-up 7-14 days post last dose):
 - a. Oral contraceptive
 - b. Injectable progesterone
 - c. Subdermal implant
 - d. Spermicidal foam/gel/film/cream/suppository
 - e. Diaphragm with spermicide
 - f. Copper or hormonal containing IUD
 - g. Sterile male partner vasectomized > 6 month pre-dosing.
- 10. Evidence of a personally signed and dated informed consent document indicating that the subject has been informed of all pertinent aspects of the study
- 11. Subjects must be willing and able to comply with scheduled visits, treatment, laboratory tests and study procedures.

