Subjects will return at months 1, 2, 3, and 4 for interim medical history, body weight, HbA1c, and FPG. Postural blood pressure measurements will be obtained with the subject lying down and then after standing for 5 minutes at each of the visits. At month 4, all of the baseline studies detailed above will be repeated.

All tests will be performed in the Clinical Research Center at the Texas Diabetes Institute/University of Texas Health Science Center, San Antonio.

Number Of Subjects

Planned enrollment = 15

Primary Subject Characteristics at Enrollment

T2DM male or female subjects between the ages of 30 and 70 years with HbA1c between 7.5-10% on a diabetes therapeutic regimen consisting of stable doses of either exenatide (2 mg/week) or liraglutide (1.2-1.8 mg/day) for at least 90 days prior to enrollment with or without metformin and/or pioglitazone and no other glucose lowering agents.

Study Treatments

Cycloset, 0.8 mg/day, with the dose increased by 0.8 mg/day every week to a maximum of 3.2 mg/day, or as tolerated to a minimum dose of 2.4 mg/day, added on to usual diabetes therapy consisting of a stable dose for at least 90 days of exenatide (2mg/week) or liraglutide (1.2-1.8 mg/day). Subjects must be on either exenatide or liraglutide as part of their standard care to be eligible for study participation.

Study Endpoints

The primary endpoint is the effect of Cycloset on glycemic control and postprandial glucose metabolism.

Secondary endpoints include the effects of Cycloset on endothelial function, aortic compliance,, body weight composition, blood pressure and markers of inflammation and oxidative stress.

Statistical Procedures

Sample Size Calculation: Assuming that Cycloset will cause a 0.6% reduction in HbA1c, we computed that 15 subjects provide 90% power to detect a 0.6% decrease from a baseline HbA1c of $8.0 \pm 0.5\%$ at an alpha of 0.05.

A statistical analysis plan (SAP), providing details of the analyses and presentation structure of the results, will be developed and finalized before the database is locked.

STUDY SCHEDULE

	Screening Period					Treatment Period (16 weeks)						
Data collected and/or action	Visit 0*	Visit 1*	Visit 2	Visit 3	Phone call 1	Phone call 2	Phone call 3	Visit 4	Visit 5	Visit 6	End of Study Visit 7 ^α	End of Study Visit 8 ^α
	Week -3 to -1	Week 0 (baseline)	Visit 1 +7-10 days	Visit 2 +3-5 days	Day 7	Day 14	Day 21	1 Month	2 Months	3 Months	4 Months	Visit 7 +3-5 days
Informed Consent	Х											

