4.3 EXCLUSION CRITERIA

- 1. Recent (i.e., within three (3) months prior to Screening) evidence or medical history of unstable concurrent disease such as: documented evidence or history of clinically significant hematological, endocrine, pulmonary, gastrointestinal, cardiovascular, hepatic, psychiatric, immunological, or clinically significant neurological disease.
- 2. No history of T2DM
- 3. BMI of less 24 and greater 40 kg/m2
- 4. Unstable body weight (change of greater than ±3-4lbs over the preceding 3 months
- 5. Subjects not currently receiving exenatide or liraglutide
- 6. Subjects participating in an excessively heavy exercise program
- 7. Subject with a feeding/sleeping schedule different from a daytime feeding/night time sleeping schedule
- 8. Subjects taking medications known to alter glucose metabolism (with the exception of any combination of metformin,pioglitazone, sulfonylureas, and insulin) or which affect brain neurosynaptic function are excluded.
- 9. Subjects with evidence of major organ system disease as determined by physical exam, history, and screening laboratory data
- 10. Pregnant subjects or subjects unwilling to use birth control during their study enrollment
- 11. Blood donation of approximately 1 pint (500 mL) within 8 weeks prior to Screening 12. Subjects that are allergic to bromocriptine or any of the other ingredients in Cycloset, or take ergot medicines, breastfeeding or have history of syncope or Type 1 diabetes mellitus0
- 12. Other severe acute or chronic medical or psychiatric condition or laboratory abnormality that may increase the risk associated with study participation or investigational product administration or may interfere with the interpretation of study results that, in the judgment of the investigator, would make the subject inappropriate for entry into this study subjects of reproductive potential

Female subjects must not become pregnant during the study. Absence of pregnancy must be checked by serum pregnancy testing at the screening visit (Visit 0).

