5 STUDY TREATMENTS

5.1 DETAILS OF STUDY TREATMENTS

All subjects will receive Cycloset, 0.8 mg/day, with the dose increased by 0.8 mg/day every week to a maximum of 3.2 mg/day, or as tolerated to a minimum dose of 2.4 mg/day, added on to usual diabetes therapy consisting of a stable dose for at least 90 days of exenatide (2mg/week) or liraglutide (1.2-1.8 mg/day). Subjects must be on either exenatide or liraglutide as part of their standard care to be eligible for study participation. Subjects will maintain their maximum tolerated dose of Cycloset for the duration of the study.

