5.4 RUN-IN MEDICATION

There is no run-in period prior to enrollment. Subjects will remain on their current regimen of either exenatide or liraglutide. No medications known to alter glucose metabolism (with the exception of metformin and/or pioglitazone),or which effect brain neurosynaptic function are allowed.

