6.2 PRIOR AND CONCOMITANT TREATMENTS

All treatments being taken by the subjects on entry to the study or at any time during the study in addition to the study drug are regarded as concomitant treatments and must be documented on the appropriate pages of the case report form.

Concomitant medications should be kept to a minimum during the study and adhere to the inclusion/exclusion criteria described above. However, if these are considered necessary for the subject's welfare and are unlikely to interfere with the investigational products, they may be given at the discretion of the investigator and recorded in the case report form.

Subjects on systemic corticosteroids will be excluded.

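### The 90-day stable-dose condition before baseline HbA1c covers only exenatide or liraglutide, so a recent change in another permitted glucose-lowering drug can be counted as Cycloset effect

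*Combined protocol and SAP*

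**What the plan says.** **Stability before entry.** Inclusion criterion 5 in section 4.2 requires "Subjects currently receiving a stable dose of exenatide (2mg/week) or liraglutide (1.2-1.8 mg/day) for at least 90 days prior to determination of baseline A1C". Section 5.1 repeats the condition for the same two drugs: "usual diabetes therapy consisting of a stable dose for at least 90 days of exenatide (2mg/week) or liraglutide (1.2-1.8 mg/day". The Protocol Outline (Primary Subject Characteristics) also attaches stable doses and the 90 days to exenatide or liraglutide.

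**Other background drugs.** The lists differ:
- Protocol Outline: "with or without metformin and/or pioglitazone and no other glucose lowering agents".
- Section 5.4: glucose-altering drugs are barred "with the exception of metformin and/or pioglitazone".
- Exclusion criterion 8 in section 4.3: the bar applies "with the exception of any combination of metformin,pioglitazone, sulfonylureas, and insulin".

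None of these gives a minimum duration or a stable dose for the drugs it allows.

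**During the study.** Section 5.4 states that there is no run-in and that "Subjects will remain on their current regimen of either exenatide or liraglutide". Section 6.2 says: "Concomitant medications should be kept to a minimum during the study and adhere to the inclusion/exclusion criteria described above". If further drugs are judged necessary for the subject's welfare and unlikely to interfere with the investigational products, "they may be given at the discretion of the investigator and recorded in the case report form". Section 9.1 provides for evaluation for withdrawal and rescue after two consecutive fasting glucose values above 275 mg/dl once titration is complete. Withdrawn subjects are referred to their own physician for medication adjustment.

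**Measure and analysis.** Section 7.3.1 makes change from baseline in HbA1c and in postprandial glucose metabolism the primary efficacy data. Section 10.1 defers analysis detail to a SAP to be finalised before database lock. No rule for background-drug changes is given.

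**The concern.** The authors tied 90 days of stability to the baseline HbA1c, presumably because HbA1c takes time to settle after a treatment change. That reasoning applies equally to metformin, pioglitazone or any other permitted glucose-lowering drug, but the condition stops at exenatide and liraglutide. Someone whose metformin was raised, or who started pioglitazone, two weeks before screening would meet the criteria as written.

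In a randomised trial such changes would be expected to balance between arms and drop out of the comparison. Here there is one open-label group, and the estimate is the mean within-subject change, so a fall caused by another drug is added directly to the apparent effect of Cycloset. Entry requires HbA1c of 7.5% to 10.0% on current therapy, so a recent intensification is more plausible than a reduction and the bias would more plausibly favour Cycloset. That direction is a judgement; the documents do not state it.

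**Working it through.** **1. The plan's own figure.** Section 10.3: 15 subjects, 90% power, a 0.6-point fall, SD 0.5, alpha 0.05. The two-sample normal formula reproduces it: n = 2 × 0.5² × (1.960 + 1.282)² / 0.6² = 14.6, rounded up to 15, with power 90.8% at n = 15. For one group this equals a paired z-test with SD of change 0.5 × √2 = 0.707. The plan gives the spread of baseline HbA1c, not the SD of change, so both 0.5 and 0.707 are used below. Nothing in this point disputes the sample size.

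**2. Timing of baseline.** In the study schedule, HbA1c is marked at Visit 0 and then not until Visit 4.
- Visit 0 to Visit 1: 1 to 3 weeks, or 7 to 21 days.
- Visit 1 to Visit 2: 7 to 10 days.
- Visit 2 to Visit 3 (first Cycloset dose): 3 to 5 days.
- Visit 0 to first dose: 7 + 7 + 3 = 17 days to 21 + 10 + 5 = 36 days, before visit windows.

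A drug changed shortly before Visit 0, or in this gap, can act on HbA1c after the baseline value and through month 4.

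**3. Shift in the mean.** If m of 15 subjects have a background change that lowers HbA1c by d points after baseline, the mean shifts by m × d / 15. The documents give neither m nor d. The ranges m = 1 to 3 and d = 0.5 to 1.0 are assumptions.

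| m | shift at d = 0.5 | shift at d = 1.0 | share of 0.6 |
|---|---|---|---|
| 1 | 0.5/15 = 0.03 | 1.0/15 = 0.07 | 6% to 11% |
| 2 | 1.0/15 = 0.07 | 2.0/15 = 0.13 | 11% to 22% |
| 3 | 1.5/15 = 0.10 | 3.0/15 = 0.20 | 17% to 33% |

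These are upper values for each m and d, because they place the whole effect after the Visit 0 sample. Any part already present in the baseline HbA1c does not count.

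**4. Effect on the test.** Simulated two-sided one-sample t-test, n = 15, true Cycloset effect zero. The nominal chance of a significant fall is 2.5%.

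| m | SD of change 0.5 | SD of change 0.707 |
|---|---|---|
| 1 | about 4% | 3% to 4% |
| 3 | 8% to 14% | 6% to 11% |

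One affected subject changes little; three would matter.

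**5. Whether another section closes the gap.** Section 6.2 sends the reader back to the eligibility criteria, which allow these drugs with no stability condition. Its proviso concerns interference with the investigational products and does not clearly extend to interference with the endpoint. Section 9.1 acts only above its fasting-glucose trigger and after titration. Neither reaches a change made before baseline.

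**The case against.** Changes during treatment are not simply open. Section 6.2 asks that concomitant drugs be kept to a minimum and limits additions to those needed for the subject's welfare. Section 9.1 suggests that glycaemic adjustment was expected after withdrawal. Section 6.2 already requires treatments at entry and on study to be documented, and a sensitivity analysis can still be written into the pending SAP. All of this stands. A reader might infer from the missing dose rule that sites may adjust background therapy freely on study, but the documents do not support that. What remains is narrower: on-study changes are discouraged, not excluded, and have no analysis rule.

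The Outline could also be read as requiring the whole regimen to be stable. Grammatically, though, the stable doses belong to exenatide or liraglutide, and sections 4.2 and 5.1 confirm this. The ambiguity is a reason to clarify; it does not close the gap.

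The size is assumed throughout, and the 33% figure needs three of 15 subjects at the largest assumed effect. That is correct. A reader might conclude that background changes could account for most of the planned 0.6-point effect, but nothing in the documents indicates that so many subjects would be affected.

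The same argument could be extended to blood-pressure and lipid drugs and the secondary endpoints. The documents give nothing from which to size that, so it is not part of this point.

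Finally, the uncontrolled open-label design limits attribution more than this gap does, and no eligibility wording cures that. This is the main reason for the moderate severity.

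**Conclusion.** The point holds in a limited form. The pre-baseline stability condition omits every permitted background glucose-lowering drug except exenatide and liraglutide, and the single-arm change-from-baseline measure has no means of removing the result. The mean HbA1c change could be shifted by at most 0.03 to 0.20 point (6% to 33% of the planned 0.6) if 1 to 3 of 15 subjects are affected by 0.5 to 1.0 point each. Both ranges are assumptions, and the shift is smaller to the extent that baseline already reflects the change. The true frequency may be zero.

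Separately, the lists of permitted background drugs contradict each other: exclusion criterion 8 admits sulfonylureas and insulin, while the Outline and section 5.4 do not. These passages must be reconciled, because the stability condition needs a settled list to refer to.

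Severity: should-fix. A reader might treat this as a defect that invalidates the primary result; the unknown frequency, the probably modest shift and the partial safeguards in sections 6.2 and 9.1 do not support that.

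**What to change.** 1. Reconcile the Protocol Outline, exclusion criterion 8 and section 5.4 on which background glucose-lowering drugs are permitted. Which list is right is for the sponsor and investigator to decide.
2. Extend the 90-day stable-dose condition in inclusion criterion 5 to every background glucose-lowering drug on the reconciled list, and align the Outline and section 5.1.
3. Pre-specify in the SAP a sensitivity analysis of change in HbA1c and meal-test measures that excludes or flags data collected after any background glucose-lowering start or dose change. Section 6.2 already requires these treatments to be documented; the record should carry the date of each change.
4. State consistently in sections 5.4, 6.2 and 9.1 how background doses are handled on study. The content of that rule is for the sponsor and investigator.

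Cost: a short amendment and one SAP paragraph, with no change to the sample size. A few candidates with a recent change would enter later. Excluding data after a change leaves fewer than 15 subjects in the sensitivity analysis, so it should be reported beside the main result and not in place of it.
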